The USFDA licensed 23-valent pneumococcal polysaccharide vaccine covers about 90% of circulating serotypes in Bangladesh (9). It produces high levels of antibody responses in adults (12). A recent study in Bangladesh showed that maternal immunization with the 23-valent polysaccharide pneumococcal vaccine, was safe and immunogenic and protective levels of antibodies (>0.15µg/mL) were observed in the infants' blood up to 22 weeks of age (13). Maternally transferred antibodies play an important role in infant protection, but the antibodies are short lived and may not fully cover the period of high risk. Maternal immunization does not produce impaired responses either with maternal anti-tetanus toxoid (TT) (a protein antigen) or with other polysaccharides as *H. influenzae* B (Hib) in infants (14). This may also induce the effect of priming in the newborn.

Vaccine efficacy depends on the prevalence of the serotypes in the vaccine, the age at which the children become immuno-competent to the predominant serotype, and the naturally acquired immunological response of the children to the important serotypes at the time of immunization (15). In developing countries, the serotypes that cause invasive disease are more likely to be ones that evoke a good immune to immunization in young children (16). Polysaccharide vaccines co-valently linked to a carrier protein are immunogenic in young infants from an early age(15). Clinical trials of the 2,5,7 & 9- valent glycoprotein conjugate pneumococcal vaccine have been conducted in young children both in developing and in developed countries and found to be safe and immunogenic when given along with routine immunization

(17-23). The serotypes in the 7 –valent CRM $_{197}$ product would cover \sim 60% of circulating serotypes here (24).

The proposal is to conduct a prospective randomized, blinded, controlled comparative trial of safety and immunogenicity of 2 US FDA licensed pneumococcal vaccines. Women will be immunized around 32 weeks gestation and infants at birth. To-date no studies have examined the immunogenicity and safety of the conjugate pneumococcal vaccine with maternal immunization.. Globally early infant deaths remain a significant problem, which cannot be addressed with current EPI strategies, even with new vaccines. This project builds on results of a previous study and will build capacity for vaccine evaluation in Bangladesh.

RESEARCH DESIGN AND METHODS:

Study Design:

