A randomized double-blind controlled immunogenicity trial will be conducted in Dhaka in collaboration with private and public facilities providing maternity health care services. In this study mothers will be randomized to receive either the pneumococcal (study) or the meningococcal (control) vaccine All infants will receive the glycoprotein conjugate pneumococcal vaccine.

Setting and Population:

This trial will be carried out in Dhaka, in collaboration with three private and public facilities providing maternity health care services. Pregnant women belonging to the middle-class come to these clinics for ante-natal care and delivery. Healthy pregnant women in the third trimester and their infants will be enrolled after signing informed consent forms. The study population will be pregnant women residing in Dhaka, Bangladesh. Our obstetrical co-investigators have helped us conduct our earlier studies with 180 women. They will again inform their registered patients of the purpose and of the trial, and refer them to our project staff assigned to that clinic. Project staff will provide a detailed explanation of the purpose, procedure, risk and benefits of the trial, answer any questions and then obtain signed informed consent of participation. Assignment to study groups will be instituted as soon as the mother gives concurrence to enroll into the study.

Selection criteria:

Inclusion criteria:

- 1. Women in third trimester of pregnancy with normal medical and obstetric history and physical examination and aged >15 and <40.
- 2. Women who plan to deliver in Dhaka and who plan to remain in Dhaka for the next 12 months.

Exclusion criteria:

- 1. Women with systemic disease as diabetes, hypertension, etc.
- 2. Women with known history of previous complicated pregnancy.
- 3. Women with previous history of preterm delivery and repeated abortions.
- 4. Women with previous history of birth with congenital anomalies.
- 5. Women with hypersensitivity reactions to vaccination.
- 6. Women with receipt of pneumococcal or meningococcal vaccine in last 3 years.

Study Procedure:

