One hundred and eighty healthy pregnant women in their third trimester will be enrolled after informed consent. Each will be given a unique identification number, which will indicate the study group she is assigned to. The numbers assigned will be from a pre-prepared list of numbers. Randomization will be a one step block design of 4 to ensure that in each block the groups are equally represented. This will entail in the study groups will be randomised to the receiving the pneumococcal polysaccharide vaccine (study) and those in the control study groups meningococcal vaccine (25). All infants will receive the conjugate pneumococcal vaccine at 6, 10 and 14 weeks of age (Appendix 1). Both these polysaccharide vaccines have been shown to be safe in our hands in published studies in Dhaka (13,25)

The design ensures that timing of blood specimens is parallel in the 4 groups, so direct comparison of each intervention can be made. For purposes of masking, every mother receives an injection of either pneumococcal or meningococcal vaccine. As such there will be total masking from the point of safety and side effect reporting in infant immunization. The major outcome variable (antibody levels) will also be determined by a completely blinded procedure.

The single dose vaccine vials will have a study label group code 1, 2, 3,4. The study coordinator will release vaccine vials to the study field staff who will take them to the obstetric practices. After determining the study group to which the mother is allocated, the field staff will note the study group allocation on the mothers' enrollment form, and write the mother's name and subject number on the vaccine vial label, and the vial number and study group in the mother's data form. After administration of vaccine, the empty study vaccine and tetanus vaccine vials will be returned to the coordinator, who will separately record the subject numbers and study group assignment against the vial numbers. Similar procedures will be followed for the study vaccines administered to the infants. The person who generates the allocation codes will not participate in subject assignment to study groups, vaccine administration, outcome assessment or data analyses, so that these processes remain blinded.

Baseline data collection

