We will test the hypothesis that conjugate pneumococcal vaccine reduces acquisition and carriage of pneumococci in infants. The main outcome measure will be the acquisition by the study children of specific pneumococcal serotypes (VT) contained in the vaccine (for 7 valent Lederle conjugate: groups/types 4, 6B, 9V, 14, 18C, 19F, 23F). The overall proportion of infants who acquire VT, the median age of acquisition, and median duration of carriage of VT will be compared between the study and control groups with appropriate statistical tests. Kaplan-Meier survival curves will be used to compare the cumulative proportions of children who acquire vaccine serotypes at each time point during this study. Bi-variate analyses will be carried out to determine the association of selected risk factors (breast feeding, crowding, etc) and the acquisition and carriage of VT and non-VT by study children. A multi-variable analysis will be done to determine the independent effects of these risk factors. The association of carriage of drug resistant pneumococci with risk factors will similarly be analyzed with bivariate and multivariable analyses. The data on carriage of pneumococci will be analyzed to determine if established carriage of VT pneumococci is shortened or otherwise influenced by the receipt of pneumococcal vaccine. If carriage of VT is reduced in recipients of pneumococcal vaccine, it will be of interest to determine if carriage of non-VT but pathogenic serotypes (types 7, 15) is increased in vaccinees, if there are adequate numbers of isolates of these types.

The association of specific serum IgG and IgA antibodies to the commonly carried pneumococcal types 6, 19, 14 and 23 with carriage of these types will be examined by chi square and regression techniques, to determine if there is an statistical association, and if there is a specific level of serum antibody which predicts reduction of carriage. We will also compare mean serum antibody titers for the most common colonizing serotypes between colonized and non-colonized infants. In mothers

who breast feed their infants, mean breast milk antibody titers against common serotypes will be compared in colonized and non-colonized infants (Appendix1)

Ethical issues

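### The between-arm carriage analysis defines vaccine type by the 7-valent conjugate that every infant receives, not by the mother's 23-valent vaccine that is randomised

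*Protocol*

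**What the plan says.** Under Study Design, "mothers will be randomized to receive either the pneumococcal (study) or the meningococcal (control) vaccine". Study Design, Study Procedure and Appendix 1 all give the conjugate to every infant, and Appendix 1 places the doses at 6, 10 and 14 weeks in both groups. The mother's vaccine is therefore the only one that differs between arms.

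The carriage part of Data analysis sets out to test whether the conjugate reduces acquisition and carriage. Its main outcome is acquisition of "specific pneumococcal serotypes (VT) contained in the vaccine (for 7 valent Lederle conjugate: groups/types 4, 6B, 9V, 14, 18C, 19F, 23F". The proportion acquiring VT, the median age at acquisition and the median duration of carriage "will be compared between the study and control groups with appropriate statistical tests". If VT carriage is lower in vaccine recipients, and enough isolates exist, the plan will also "determine if carriage of non-VT but pathogenic serotypes (types 7, 15) is increased in vaccinees".

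The Background states that the "23-valent pneumococcal polysaccharide vaccine covers about 90% of circulating serotypes in Bangladesh" and puts the 7-valent product at about 60%. Laboratory procedures assessment lists types 1, 6, 19 and 23 as vaccine types for the antibody assays. Type 1 is not among the seven conjugate types. The protocol nowhere defines VT by the 23-valent vaccine, splits non-VT into types inside and outside it, or lists the 23 types.

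**The concern.** In a between-arm comparison, the vaccinated group can only be the infants of mothers given the 23-valent vaccine, because every infant has the conjugate. The VT label nevertheless follows the vaccine that is the same in both arms. Followed as written, an infant who acquires a type that is in the 23-valent but not the 7-valent vaccine is scored non-VT, although only the study-group mother was immunised against that type.

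Two things are at stake. First, the main carriage outcome leaves out types on which the maternal vaccine could act. Secondary objective 4 names antibody from maternal as well as infant immunisation. Swabs are taken at birth and at 6 weeks, so acquisition before the first conjugate dose can reflect only the maternal vaccine, yet it is scored by the conjugate's list. Second, the replacement check could count as replacement a type that the randomised vaccine itself covers, and would then be hard to interpret in either direction.

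**Working it through.** **The plan's own carriage figure.** Sample size estimate claims 90% power with 90 per group for 80% v 50% colonised. With the two-sided 5% two-proportion normal approximation, power = Φ{[0.30·√90 − 1.96·√(2·0.65·0.35)]/√(0.80·0.20 + 0.50·0.50)} = Φ{(2.846 − 1.322)/0.640} = Φ(2.38) = 99.1%. At 63 completers per group it is 95.1%. The stated 90% is conservative. It does not say which types count as colonisation, so it neither supports nor weakens this point.

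**Coverage arithmetic.** Inputs, both from the Background: c23 = about 0.90 and c7 = about 0.60 of circulating types.

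- Scored non-VT under the 7-type rule: 1 − c7 = 0.40.
- Outside the 23-valent vaccine: 1 − c23 = 0.10.
- Scored non-VT but covered by the 23-valent vaccine: c23 − c7 = 0.30. This is exact if all seven types are in the 23-valent vaccine, and a minimum otherwise.
- Share of non-VT covered by the randomised vaccine: 0.30/0.40 = 75%.
- Share of the randomised vaccine's coverage left out of VT: 0.30/0.90 = 33%.

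**Sensitivity to rounding (assumed ±5 points on each figure).**

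| c23 | c7 | (c23 − c7)/(1 − c7) | (c23 − c7)/c23 |
|---|---|---|---|
| 0.85 | 0.65 | 57% | 24% |
| 0.85 | 0.55 | 67% | 35% |
| 0.90 | 0.60 | 75% | 33% |
| 0.95 | 0.65 | 86% | 32% |
| 0.95 | 0.55 | 89% | 42% |

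Most of what is scored non-VT stays covered by the randomised vaccine throughout.

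**Illustration of power, under assumed effects only.** Let A be any-type acquisition in controls, H = −ln(1 − A), and s the share of types counted (0.6 or 0.9). Acquisition is 1 − exp(−sH) in controls and 1 − exp(−0.5·sH) in the study group. This assumes that the maternal vaccine halves the hazard equally for all types it covers (including the seven), that acquisition is proportional to circulating share, and that the conjugate effect is equal in both arms. None of these comes from the protocol. The test is the two-proportion test above.

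| A | Types counted | Control v study | Power, 63 per group | Power, 90 per group |
|---|---|---|---|---|
| 80% | 7-valent | 61.9% v 38.3% | 76% | 89% |
| 80% | 23-valent | 76.5% v 51.5% | 84% | 94% |
| 65% | 7-valent | 46.7% v 27.0% | 63% | 79% |
| 65% | 23-valent | 61.1% v 37.7% | 76% | 89% |

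Under these assumptions the 7-type rule costs 5 to 13 percentage points of power.

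**The case against.** The strongest reply is that the 7-type comparison is sound. It is a randomised contrast on seven named types, and it answers a coherent question for a trial about interference: does maternal immunisation change carriage of the types the infant is actively immunised against? That stands. A reader might infer that the VT comparison is misclassified or invalid; the documents do not support this. It is incomplete for the maternal vaccine, not wrong for the seven types.

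A reader might also infer that the plan would report a fall in non-VT carriage while uncovered types were rising. That needs a between-arm comparison of the whole non-VT class, which the protocol does not state. Its replacement check names only types 7 and 15 and is conditional on lower VT carriage and enough isolates. The stated analysis of non-VT as a class concerns risk factors such as breast feeding and crowding. Whether types 7 and 15 are in the 23-valent vaccine cannot be settled from the protocol.

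The 75% is nominal. It subtracts two rounded figures from different cited sources, and both describe circulating rather than carried types. The protocol gives 6, 19, 14 and 23 as the commonly carried types, all represented in the conjugate, so VT may make up more than 60% of carriage and the omitted share may be smaller than a third.

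Finally, the root may be the hypothesis sentence, which names a vaccine that is not randomised. The two should be corrected together. Rewording the hypothesis alone, however, leaves the list of seven types in place. Nor is this simply a detail left for the analysis plan, because the protocol has already fixed the definition.

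**Conclusion.** The point holds as a badly fixed classification rule, not as an invalid comparison. VT follows a vaccine given in both arms. Nominally 75% (57% to 89%) of circulating types scored non-VT are covered by the randomised vaccine, and about a third (24% to 42% over the same range) of what that vaccine covers is outside the main carriage outcome. These figures rest on the Background's approximate coverage values, and on treating circulating types as a guide to carried types. The power differences are illustrative only.

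Types called non-VT, including 7 and 15, cannot be read as replacement until they are shown to lie outside the 23-valent vaccine. The inclusion of type 1 among the vaccine types for the assays shows that the term itself is not used consistently. Carriage is the fourth secondary objective, so the primary immunogenicity comparison is unaffected. The correction is still worth making because it is cheap.

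**What to change.** For the between-arm carriage analysis, list the 23 types and place each isolate in one of three classes:

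- (a) 7-valent types;
- (b) types in the 23-valent vaccine only;
- (c) types in neither vaccine.

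Report acquisition of any 23-valent type (a + b) between arms alongside the 7-type result, and state in advance which is the main one. Limit the replacement analysis to class (c), and check types 7 and 15 against the 23-valent list before calling them non-VT. Reword the carriage hypothesis so that it refers to the maternal vaccine, and use the term vaccine type in the same sense in Laboratory procedures assessment and Data analysis.

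The cost is a few lines of text and one recoded variable, since isolates are serotyped in any case. The downside is that class (c) covers only about 10% of circulating types, so the replacement estimate will be imprecise and should be presented as such.

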
SUMMARY OF ANALYSES

Objectives	Variables	Analysis
Primary: 1a	antibody titer:	t-test, chi square
Immunogenicity	GMT, $\% > 0.15$, $1 \mu g/ml$	regression
Primary: 1b Safety	% reaction rates	chi square
Secondary: 2	cord, final antibody:	correlation
Maternal-filial	GMT, % >0.15, 1 μg/ml	coefficient
Secondary: 3	cord, final antibody; GMT;	means,
EPI schedule	GMT, % >0.15, 1 μg/ml	proportions
Secondary: 4	cord, final antibody; GMT;	chi square,
NP colonization	% colonization rates	regression

Appendix 3 Two-Sample T-Test Power Analysis

Numeric Results for Two-Sample T-Test

Null Hypothesis: Mean1=Mean2. Alternative Hypothesis: Mean1>Mean2 The standard deviations were assumed to be known and equal.

		Α	llocation	•					
Power	N1	N2	Ratio	Alpha	Beta	Mean1	Mean2	S1	S2
0.80286	63	63	1.00	0.02500	0.19714	0.559	0.258	0.601	0.601
0.80514	50	50	1.00	0.05000	0.19486	0.559	0.258	0.601	0.601

Two-Sample T-Test Power Analysis

Numeric Results for Two-Sample T-Test

Null Hypothesis: Mean1=Mean2. Alternative Hypothesis: Mean1>Mean2 The standard deviations were assumed to be known and equal.

			Allocation						
Power	N1	N2	Ratio	Alpha	Beta	Mean1	Mean2	S1	S2
0.80000	40	40	1.00	0.02500	0.20000	0.559	0.182	0.601	0.601
0.80000	50	50	1.00	0.02500	0.20000	0.559	0.222	0.601	0.601
0.80000	60	60	1.00	0.02500	0.20000	0.559	0.251	0.601	0.601
0.80000	70	70	1.00	0.02500	0.20000	0.559	0.274	0.601	0.601
0.80000	80	80	1.00	0.02500	0.20000	0.559	0.293	0.601	0.601
0.80000	90	90	1.00	0.02500	0.20000	0.559	0.308	0.601	0.601
0.80000	100	100	1.00	0.02500	0.20000	0.559	0.321	0.601	0.601
0.80000	40	40	1.00	0.05000	0.20000	0.559	0.225	0.601	0.601
0.80000	50	50	1.00	0.05000	0.20000	0.559	0.260	0.601	0.601
0.80000	60	60	1.00	0.05000	0.20000	0.559	0.286	0.601	0.601
0.80000	70	70	1.00	0.05000	0.20000	0.559	0.306	0.601	0.601
0.80000	80	80	1.00	0.05000	0.20000	0.559	0.323	0.601	0.601
0.80000	90	90	1.00	0.05000	0.20000	0.559	0.336	0.601	0.601
0.80000	100	100	1.00	0.05000	0.20000	0.559	0.347	0.601	0.601

M2 vs N1 by Alpha with M1=0.559 S1=0.601 S2=0.601 Power=0.80 N2=N1 1-Sided T Tes
